### **9.7. Clinical Events Committee (CEC)**

An independent Clinical Events Committee (CEC) will be established for this study. The CEC will have at least two members who are qualified to review adverse event data from this study. The CEC will be established and operate according to a charter defined prior to the initiation of the trial. The CEC (Baim Institute) will review individual adverse events that meet the following criteria:

- Adverse events that are categorized by the investigator on the eCRF as “associated with the target artery and/or the ipsilateral leg (not the contralateral side)”; OR
- Adverse events in the other two categories (“associated with the contralateral access site” or “systemic adverse events”) that are categorized by the investigator as possibly, probably or definitely device-related.

In addition, the medical monitor will review programmed listings for all AEs that are not captured by the criteria above to identify any additional AEs that appear to meet the endpoint definitions and should be reviewed and adjudicated by the CEC.

For each AE reviewed, the CEC may adjudicate its device-relatedness. The CEC will determine if each reviewed adverse event meets the definition of a Major Complication or a Minor Complication or neither definition. In addition, the CEC will adjudicate each AE as to whether it is a VARC-2 Major Vascular Complication. Analysis of the primary and secondary safety endpoints will be based on CEC-adjudicated data.

### **9.8. Data & Safety Monitoring Committee (DSMC)**

A Data and Safety Monitoring Committee (DSMC) will be established for this study. The DSMC will be independent from the Sponsor and the study investigators. It will consist of at least three (3) members: a statistician, an interventional cardiologist and a vascular surgeon; the latter two members must have extensive experience with large-bore cardiovascular interventions. The

DSMC will be established and operate according to a charter defined prior to the initiation of the trial. The DSMC will review cumulative adverse event data and will recommend study termination if safety concerns warrant such action. If the DSMC believes it is possible to predict adverse events, guideline criteria for recommending study termination will be established before enrollment in the study begins. The DSMC will meet, either by phone or face-to-face, at least 2 times during the study in order to assure close and timely monitoring of adverse events and outcomes.

## 10 Medication

There are no prohibited medications for this clinical investigation.

Only the following medications will be recorded on the eCRF: cardiovascular medications (e.g., anti-hypertensives, anti-arrhythmics, etc.), anti-coagulants, anti-thrombotics and anti-platelets. This includes such medications being taken at baseline through 60-day follow-up, inclusive of medications given in the cath lab.

For these medications, the following information will be recorded:

- Name of medication
- Indication
- Being taken prior to study enrollment (Yes/No)
- Being taken due to study adverse event (Yes/No)
- Ongoing at study end (yes or no)

## **11 Vulnerable Population**

The intended patient population of this clinical investigation does not meet the criteria of vulnerable population as defined in ISO 14155, Section 3.44.

## **12 Data Management**

### **12.1. Case Report Forms**

The Investigator is responsible for ensuring the completeness and accuracy of all study documentation, including the eCRFs. All clinical study data must be reported on electronic case report forms (eCRF) provided by the Sponsor.

The investigator must review, and electronically sign off the eCRFs as indicated on the form; these responsibilities cannot be delegated to another person. It is the investigator's responsibility to comply with regulatory requirements including, but not limited to, the maintenance of accurate, complete and current records relating to the eCRFs.

Queries may be generated by the data management department of the CRO or by the monitor during a monitoring visit directly in the eCRF. In general, queries should be resolved by making additions or corrections to the eCRF.

### **12.2. Data Management**

The CRO's monitors will review the data against the original source documents and ensure any noted discrepancies are resolved by the investigational site. Subject data will be compared to information originally recorded on source documents related to the trial (i.e. professional notes, laboratory reports, investigation-specific worksheets, etc.).

All information collected in the eCRFs will be entered directly into a secure database. The database design and installation will be validated prior to use.

The details of data review, database cleaning and data querying are described in a Data Management Plan (DMP). This plan may be updated throughout the investigation as amended data management requirements and investigation-specific data conventions are determined.

A comprehensive eCRF Completion Guideline for participating investigational sites will be developed to describe general instructions on eCRF completion.

Data entered by investigational sites will be reviewed on an ongoing basis to ensure adequate query resolution and identify and query adverse events, protocol deviations, and any other ambiguous data points.

### **12.3. Data Retention**

Record retention period will be determined by country and/or site-specific requirements. At a minimum, records must be retained for at least 2 years beyond the date of PMA approval of the MANTA device or 2 years beyond the termination of this study, in the case of the Sponsor's decision not to pursue a PMA.

### **12.4. Other Aspects of Clinical Quality Assurance**

The study will be conducted and monitored by the CRO under the sponsorship of Essential Medical, Inc. (see next section).

The Sponsor, or the Sponsor's representative, may conduct audits at the investigational sites. Audits may include, but are not limited to, device supply, presence of required documents, the informed consent process, and comparison of eCRFs with source documents. The investigator agrees to participate with audits conducted at a reasonable time, in a reasonable manner.

The U.S. Food and Drug Administration may inspect investigational sites if warranted. The EU and Canadian ECs and competent authorities may also audit investigational sites that are involved in this study.

## **13 Clinical Monitoring**

### **13.1 Clinical Research Organization**

Study monitoring functions will be performed by clinical monitors from a qualified independent clinical research organization (CRO) in compliance with recognized applicable U.S. regulations (21 CFR Part 812 [Investigational Device Exemptions], 21 CFR Part 50 [Protection of Human Subjects] and 21 CFR Part 56 [Institutional Review Boards]), Good Clinical Practice, ISO 14155:2011 and recommendations guiding physicians in biomedical research involving human subjects adopted by the 18th World Medical Assembly, Helsinki, Finland, 1964. The CRO will oversee progress of the investigation and work with research coordinators to ensure adherence to the study protocol and informed patient consent obligations.

### **13.2 Monitoring**

The Sponsor/CRO has responsibility for performing site visits prior to the start of and during the study to monitor data collection forms for accuracy and completion and for verifying the report of any adverse events. The monitor will also review the site device inventory, storage conditions and device dispensing records to verify device accountability.

On-site monitoring visits include a pre-study visit, periodic visits, and a final visit at the close of the study.

The pre-study visit is intended to review the Investigational Plan with the investigator and to assure that the investigator has:

- Appropriate training, facilities, patient load, time, and willingness to comply with study requirements.
- Approval of the IRB for the Investigational Plan.
- All study documentation and required records on site.
- Assumed responsibility for the investigation at her/his center.

Periodic visits are intended to assess:

- Investigator's adherence to the Investigational Plan.
- Maintenance and tracking of records, reports and investigational devices.
- Source documents for accuracy, completeness, and legibility.

During these periodic visits, the monitor is required to: 1) assess the progress of the study toward meeting study objectives, 2) identify any concerns that stem from observations of device performance and/or review of the investigator's subject records, 3) review study management and informed consent documents, and 4) ensure accountability of all investigational devices and subjects that have been treated under the study. The monitor's final on-site visit at completion of the study is intended to assure that all the data and investigational devices have been properly collected and to have a closing meeting with the investigator and her/his staff members.

Reports of the on-site visits will be made by the monitor and should include resolution of concerns, completion of appropriate follow-up activities, completion of assigned tasks, and any necessary corrective actions. At the close of the study, the monitor will prepare a final monitoring report.

### **13.3 Initial Procedures**

The monitor and/or company representatives may attend the initial procedures utilizing the device to provide assistance with device training, study management issues, including compliance with credentialing, study documentation, product inventory, and specific record keeping and reporting requirements. A data review with the investigator by the study monitor will be held after a few initial procedures to assure adherence to the study protocol.

### **13.4 Review of Study Documents**

The monitor will review completed data forms and study documentation for accuracy, completeness, and protocol compliance. The following documents will be audited:

- (1) Investigator Agreement signed by the investigator, indicating his/her agreement to participate in the investigation and willingness to comply with all study requirements.
- (2) Case Report Forms will be reviewed for errors, omissions, internal consistency, and signature and dates in the appropriate sections. The monitor will assume responsibility for any follow-up activities that result from review of these forms. Subject informed consent documents will be reviewed for completeness.
- (3) Study Monitor Reports, including pre-study visits, initial procedure visits, on-site visits or final visits reports, submitted by a monitor-designate will be reviewed by the monitor. The monitor will assume responsibility for any corrective action.
- (4) Study Master File, including initial and ongoing IRB approvals, will be reviewed for completeness and updated as necessary. Study Master File will contain all study documents and correspondences.
- (5) Source Documents will be reviewed and compared against electronic case report forms to ensure the accuracy of the eCRFs. Source documents will also be reviewed for adverse events not reported by the investigators.

### **13.5 Device Accountability**

The Sponsor will supply each Investigator with an adequate number of investigational devices for completion of the study. The study devices may only be used for subjects enrolled into this study under the supervision of the Investigator and under the terms of the clinical protocol. The Investigator may not provide the devices to any person not authorized to use it. The Investigator will also ensure that the device components are maintained under secure storage and that the device accountability record is maintained. When instructed by the sponsor, the investigator will return any remaining devices to the sponsor. Device accountability will be checked at routine monitoring visits. This will include:

- product code
- lot number
- receipt dates
- dates and quantities dispensed including subject number
- return date to the Sponsor or destruction date (if any)

All mechanical failures, malfunctions and defects of the MANTA VCD will be recorded on the eCRF and should be reported to the Sponsor. Do not dispose of any device that malfunctions. Any used devices that have malfunctioned should be treated as biohazardous; investigational

sites will be provided with specific instructions and supplies for returning such devices. Devices may not be re-sterilized and reused. The following will be reported:

- All situations where the device physically deforms or breaks even if caused by user error.
- All situations where the device fails to move or perform as it was intended to function according to the instructions for use.
- All situations where the device is physically defective.

## **14 Protocol Deviations and Amendments**

### **14.1. Protocol Adherence and Deviations**

The study will be conducted as described in this protocol. Investigators are not permitted to deviate from this protocol except to protect the subject's rights, safety or well-being. Any deviations from this protocol must be documented by the Investigator. If an emergency situation arises in which the rights, safety or well-being of a subject may require immediate alternative intervention, the Investigator should act in the best interests of the subject. Sponsor and the site's IRB/EC must be notified immediately if this occurs. This should be followed with written confirmation that describes the emergency action and outcomes to Sponsor and the IRB/EC within 10 working days. Protocol deviations will be reviewed during monitoring visits; as appropriate, Investigators will be required to identify corrective and preventive actions to prevent further deviations. An Investigator may be disqualified from the study for repeated and/or egregious protocol deviations.

This protocol may be amended as necessary by the Sponsor. Any protocol amendments will be documented via an incremented version of this protocol with the relevant revision history. Amendments to the protocol must undergo the same approval process by the Sponsor, Investigators, IRB/ECs and regulatory authorities as the original protocol.

### **14.2. Corrective and Preventive Actions**

The Sponsor or its representatives will evaluate protocol deviations during monitoring visits. Individual event corrective and preventive actions may be recommended at that time. In addition, deviations occurring across investigational sites will be reviewed by the Sponsor on a periodic basis to determine if more global preventive actions may be required.

### **14.3. Investigator Disqualification Criteria**

The Sponsor reserves the right to terminate an investigator/investigational site for any of the following reasons:

- Failure to secure subject informed consent, including protection of personal data, prior to enrollment.
- Failure to report safety events within 24 hours of discovery to the Sponsor after learning of the event.
- Failure to report serious adverse device effects within 24 hours of discovery.
- Repeated investigational plan deviations.
- Repeated failure to appropriately complete eCRFs.
- Failure to enroll an adequate number of subjects.
- Loss of or unaccounted for investigational product inventory.

## **15 Statements of Compliance**

This clinical investigation will be conducted in compliance with the principles that have their origin in the latest version of the Declaration of Helsinki; this clinical investigation plan; U.S. 21 CFR Parts 50, 56 and 812; requirements of the approving IRBs/EC and competent authorities, including the U.S. FDA; ISO 14155:2011; the EU Medical Devices Directive 93/42/EEC Annex X – Clinical Evaluation; and other applicable regulatory requirements, whichever provides the greater protection of the individual.

This clinical investigation will not be initiated until approval has been obtained from the IRB/EC and the regulating competent authority at each site. Any additional requirements imposed by the IRB/EC or regulatory authority will be followed. No changes to the protocol will be implemented without the prior review and approval of the IRB/EC and the regulatory authority.

This protocol conforms to all the standards of Medicare coverage requirements. The MANTA subject characteristics are consistent with the Medicare population, and the results are expected to be generalizable to the Medicare population.

## **16 Publication Policy**

### **16.1. *Publication by Essential Medical, Inc.***

Essential Medical, Inc. may at any time publish the results of and information pertaining to the investigation subject only to compliance with regulatory requirements pertaining to subject protected health information.

### **16.2. *Publication by Investigational Sites***

The conditions under which an investigator may publish results from this clinical investigation in any form are defined in detail in the clinical trial agreement.

| SOPs | Standard operating procedures |
| STS | Society of Thoracic Surgeons |
| TAVR/TAVI | Transcatheter aortic valve replacement / transcatheter aortic valve implantation |
| TTA | Time to ambulation |
| TTH | Time to hemostasis |
| UADE | Unanticipated adverse device effect |
| USADE | Unanticipated serious adverse device effect |
| VARC | Valve Academic Research Consortium |
| VCD | Vascular closure device |

1 GENERAL AND TECHNICAL ASPECTS

The objective of this statistical analysis plan is to specify the planned analysis and reporting for the clinical trial protocol PSD-109, sponsored by Essential Medical, Inc. It is intended to describe the statistical methodology and data conventions to be used in the statistical programming and the creation of tables, figures, and listings.

This statistical analysis plan is based on the clinical trial protocol, PSD-109 (Rev. F), dated June 2, 2017. The format and content of the Statistical Analysis Plan (SAP) are structured to provide sufficient detail to meet the requirements specified by the International Conference on Harmonization (ICH) E9: Guidance on Statistical Principles in Clinical Trials. Note that ISO 14155:2011 does not include specified requirements for a SAP.

All programs will be written using SAS (Statistical Analysis System) version 9.4 or higher. SAS programs will be written for all tables, figures and listings. All outputs will be transferred into .rtf-files. These files will be generated separately for the tables and figures of Section 14 and the listings of Section 16.2 of the appendix of the clinical study report.

2 CLINICAL TRIAL DESIGN AND OBJECTIVES

2.1 Clinical Trial Design

This is a multi-center, prospective, single-arm clinical investigation designed to evaluate the safety and effectiveness of the MANTA vascular closure device in achieving hemostasis in femoral arterial access sites in subjects undergoing percutaneous transcatheter interventional procedures using a large-bore procedure sheath. This investigation is being conducted for purposes of supporting a PMA approval in the United States, as well as other global regulatory approvals.

A minimum of five and up to 25 clinical sites in the United States, European Union, and/or Canada will participate in the trial. Approximately 263 subjects will be treated with either the 18F MANTA device or the 14F MANTA device to yield 250 subjects available for analysis at the 30-day primary safety endpoint, accounting for a 5% loss to follow-up rate. This group is termed the Primary Analysis Cohort. In addition to these 263 subjects, up to two subjects will be enrolled per treating Investigator (the Roll-In Cohort) to allow Investigators to learn how to use the MANTA device; these subjects will be summarized separately from the Primary Analysis Cohort.

Up to 90 days prior to the scheduled index procedure, the medical records of potential study subjects are screened for selected study inclusion/exclusion criteria to determine whether the subject is a potential candidate for the study. If a candidate, the subject will then be approached prior to the index procedure and the study will be explained. If a subject agrees to the study, he/she will provide written informed consent after which time, the subject will be screened to the study baseline inclusion/exclusion criteria. If all criteria are met, during and immediately following the index procedure, the subject will be assessed for the intra-procedure exclusions to confirm continued eligibility before undergoing treatment with the MANTA device. Subjects are considered enrolled in the clinical investigation after they have provided written informed consent and have been determined to meet all eligibility criteria, including the intra-procedure exclusion criteria.

Subjects can then undergo the procedure, during which the Investigator will select the correct size of MANTA closure device, depending on the size of the femoral sheath or interventional device used for the procedure. After the procedure, subjects will be assessed for Time to Hemostasis

(the primary effectiveness endpoint) and other post-procedure evaluations. Subjects will be discharged from the hospital when deemed ready by the Investigator and will return for follow-up visits at 30 ± 7 days and at 60 ± 14 days post procedure to assess for any major or minor complications or adverse events. Subjects will undergo a clinical exam, a target femoral access site external visual assessment, a duplex ultrasound exam (no 60-day ultrasound if no findings at 30 days), and be assessed for medication use and ABI at these follow-up visits.

2.2 Clinical Trial Treatments

2.2.1 Treatment Groups

There is only one treatment group in this trial; all subjects will be treated with the MANTA vascular closure device. A minimum of 50% of subjects will be treated with the 18F MANTA device and the remainder will be treated with the 14F MANTA device. The Sponsor will monitor the study with respect to the number of subjects receiving each device to encourage recruitment of a balance of cases. There is no randomization in this investigation.

The primary analysis of the study will be performed on the Primary Analysis Cohort. The Roll-In Cohort will be analyzed separately from the Primary Analysis Cohort; the Roll-In Cohort data will not be analyzed or compared to the Performance Goals or Clinical Acceptance Criterion.

2.2.2 Blinding

Due to the physical and clinical nature of the MANTA device, neither the Investigator nor the subject will be blinded.

2.3 Clinical Trial Objectives

The objectives of this study are to evaluate the safety and effectiveness of MANTA in achieving hemostasis in femoral arterial access sites in patients undergoing percutaneous transcatheter interventional procedures using a large-bore procedure sheath.

2.4 Primary Study Hypotheses

2.4.1 Primary Safety Hypothesis

The primary safety hypothesis is that the rate of Major Complications in the Primary Analysis Cohort (the proportion of subjects with one or more Major Complications as defined in Section 2.5.1 below) within 30 days of the procedure is less than the Performance Goal of 19.9%. This Performance Goal was derived from data in the published literature on the use of single or multiple Proglide/Prostar devices in large-bore procedures and from the clinical judgment of expert advisors.

Null hypothesis: The rate of Major Complications within 30 days of the procedure is not less than the Performance Goal of 19.9%.

$$H_0: \pi \geq 0.199$$

Alternative hypothesis: The rate of Major Complications within 30 days of the procedure is less than the Performance Goal of 19.9%.

$H_A: \pi < 0.199$,

where π is the population Major Complication rate. The rate of Major Complications in subjects treated with the MANTA device within 30 days will be presented along with the exact one-sided upper 97.5% confidence bound. If this upper confidence bound is less than 19.9%, the study will have met its primary safety objective.

If more than 13 of the subjects in the Primary Analysis Cohort (5% of the 250 assumed to achieve statistical power) are lost to follow-up or die due to a reason other than a Major Complication, the Major Complication rate will also be estimated from a Kaplan-Meier rate statistical curve. Subjects lost to follow-up will be censored at the date of their last contact. Subjects who die due to a reason other than a Major Complication will be censored at their date of death. An asymptotic one-sided upper 97.5% confidence bound will be placed on the estimated major complication rate at 30 days using the estimated survival curve and the standard error formula given by Peto, Peto, and Armitage¹ in Statistical Note 6. If this upper confidence bound is less than 19.9%, the study will have met its primary safety objective.

In addition, the proportion of subjects with each individual Major Complication will be presented along with their two-sided exact 95% confidence intervals.

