5 DATA CONVENTIONS AND DEFINITIONS

5.1 Handling of Missing Data

Missing data will not be imputed for safety endpoints. However, if more than 13 subjects in the Primary Analysis Cohort either die for a reason other than a Major Complication or are lost to follow up within 30 days of treatment, then the rate of Major Complications will also be estimated by the Kaplan-Meier method, to allow for subjects who are censored before a Major Complication can be observed. See Section 2.4.1 for further details.

For effectiveness endpoints, it is highly unlikely that there will be missing data for Time to Hemostasis, Technical Success, Ambulation Success, Time to Ambulation, Treatment Success or Procedure Time. However, if any of these data are missing (i.e., in the event that Time to Hemostasis cannot be evaluated because a surgical repair must be performed), the worst value observed for any subject at the same study site within each analysis cohort, will be imputed for the missing value. Missing data for a subject in the Primary Analysis Cohort will be imputed with the worst value observed for any Primary Analysis Cohort subject at the same study site, and missing data for a subject in the Roll-In Cohort will be imputed with the worst value observed for any roll-in subject at the same study site.

No other imputations will be carried out for missing data.

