6.3.1 Adverse Events

Adverse events will be coded using MedDRA dictionary (Version 20.0) and will be classified by system organ class (SOC) and preferred term (PT). Adverse events meeting certain criteria as defined in Section 9.7 of the protocol and Section 7 below will be adjudicated by the Clinical Events Committee and be designated a Major Complication, Minor Complication, or VARC-2 Major Vascular Complication for the primary and secondary safety endpoints as applicable.

6.3.2 Primary Safety Endpoint:

The Major Complication rate is defined to be the proportion of subjects in the safety evaluation set with one or more Major Complications. The Major Complication rate will be presented along with the one-sided upper 97.5% confidence bound. If this confidence bound is less than 19.9%, the study will have met its primary safety objective.

If a significant number of subjects (>5%) are lost to follow-up or die due to a reason other than a major complication, the Major Complication rate will also be estimated as a Kaplan-Meier rate. Subjects lost to follow-up will be censored at the date of their last contact. Subjects who die due to a reason other than a Major Complication will be censored at their date of death. An exact one-sided upper 97.5% confidence bound will be placed on the estimated major complication rate at 30 days using the formula given by Peto, Peto, and Armitage⁴. If this upper confidence bound is less than 19.9%, the study will have met its primary safety objective.

Additionally, the proportion of subjects with each individual Major Complication will be presented along with their two-sided exact 95% confidence intervals.

6.3.3 Secondary Safety Endpoint:

The proportion of subjects with Minor and Major VARC-2 complications will be presented. Minor complications will be qualitatively evaluated against the CAC of 20%. Summary statistics will be reported, but no formal statistical test will be performed.

Additional Safety analyses will report the incidence of adverse events:

- Overall (i.e., regardless of severity or relationship to procedure or device)
- By severity grade as determined by the Investigator (mild, moderate, or severe):
 - **Mild:** awareness of a sign or symptom that does not interfere with the subject's usual activity or is transient, resolved without treatment and with no sequelae.
 - **Moderate:** interferes with the subject's usual activity and/or requires symptomatic treatment.

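### Above the loss trigger, the SAP lets either the crude or the Kaplan-Meier bound meet the primary safety objective, with no rule for disagreement, and the Kaplan-Meier bound is labelled both asymptotic and exact

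*SAP*

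**What the plan says.** SAP 2.4.1 presents the crude Major Complication rate with an exact one-sided upper 97.5% bound and then states: "If this upper confidence bound is less than 19.9%, the study will have met its primary safety objective". If more than 13 subjects are lost or die of another cause, "the Major Complication rate will also be estimated from a Kaplan-Meier rate statistical curve". The bound on that estimate is described as follows: "An asymptotic one-sided upper 97.5% confidence bound will be placed on the estimated major complication rate at 30 days using the estimated survival curve". Its stated basis is "the estimated survival curve and the standard error formula" of a cited source. The success sentence is then repeated word for word.

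SAP 6.3.2 has the same structure. The crude rate is "the proportion of subjects in the safety evaluation set with one or more Major Complications", followed by "If this confidence bound is less than 19.9%, the study will have met its primary safety objective". The trigger here is more than 5%, and the second bound has a different label: "An exact one-sided upper 97.5% confidence bound will be placed on the estimated major complication rate at 30 days". A second success sentence follows.

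Protocol 8.3.3 also calls the Kaplan-Meier bound exact and leaves its trigger unquantified. It has one success sentence only, placed after the Kaplan-Meier text.

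SAP 5.1 says "Missing data will not be imputed for safety endpoints", limits the trigger to losses and deaths within 30 days of treatment, and refers back to 2.4.1. SAP 8 records no change from the planned analyses.

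**The concern.** The decision rule for one of the two primary hypotheses is incomplete. Two different bounds carry the same success criterion. Nothing says whether one takes precedence, both must pass, or either will do. In an unblinded single-arm study, a choice made after the counts are known is not pre-specified, and the literal either-bound reading gives a second chance to pass at the same nominal 2.5%.

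The trigger could plausibly be met. The plan itself allows for 5% loss, and the trigger also counts unrelated deaths. The EU study in Protocol 1.4 had 4 deaths in 50 subjects (8%), none judged related to the device or procedure; 8% of 263 is about 21. Those deaths fell over a 60-day study and their timing is not given, so this is indicative only.

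The label matters less, but it is wrong in two of three places: a bound built from a survival curve and a standard error formula is not exact.

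**Working it through.** **Inputs.** Goal 19.9%, assumed rate 13%, one-sided 0.025, 80% power, 250 evaluable and 263 treated (SAP 2.4.1 and 3). Assumptions: timing of events and losses; lost subjects kept in the crude denominator as event-free; and the standard error form, because the documents do not print the cited formula. Two untransformed forms were used: Greenwood, and S×√((1−S)/number at risk at day 30).

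**Plan's own figure.** Exact upper bound = Beta⁻¹(0.975; x+1, n−x). At n = 250 at most 37 events pass; size is 2.32% and power 82.7%. The smallest n from which power stays at or above 80% is 249. The continuity-corrected normal formula gives 253. The stated 250 reproduces.

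**Crude rule at 263.** 39/263 gives 19.71% (pass) and 40/263 gives 20.13% (fail). Size with no losses is 2.09%.

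**Limiting layouts, 14 lost.**
- All lost before any event, 39 events: F = 39/249 = 15.66%; SE = √(0.1566×0.8434/249) = 2.30%; bound = 15.66 + 1.96×2.30 = 20.18% (fail). Crude passes.
- All lost after the last event, 40 events: F = 40/263 = 15.21%. Greenwood SE = √(0.1521×0.8479/263) = 2.21%, bound 19.55%. The other form, with 263−40−14 = 209 at risk, has SE 2.29%, bound 19.69%. Both pass. Crude fails.

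**Less extreme layouts.**
- 40 events, 38 at the procedure, 14 lost evenly over 30 days: crude 20.13% (fail), Kaplan-Meier 19.58-19.72% (pass). Both forms still pass at 27 lost.
- 39 events, 20 at the procedure, losses in the first week: crude 19.71% (pass). Kaplan-Meier fails from 19 or 21 lost, depending on the form, and is 20.12-20.24% at 26 lost.

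With 14 to 26 lost and 50, 80 or 95% of events at the procedure, 38 events pass on every bound and 41 fail on every bound. The band widens only in the artificial limit where all losses precede every event (38 events, 20 lost: crude 19.29%, Kaplan-Meier 20.20%).

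**Chance of landing there.** P(39 or 40 of 263) is 8.7% at a true 13%, 0.6% at 10%, and negligible at the EU study's 6%. At 13% the two bounds disagree in 0.1-1.0% of simulated trials at 5% loss and in 0.3-3.9% at 8-10% loss.

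**Type I error at a true 19.9%.** Simulation, n = 263, 200,000 trials per scenario (Monte Carlo SE 0.03-0.05 points). Loss is even over 30 days or confined to the first week; 50, 80 or 95% of events are at the procedure, the rest even over 30 days. Ranges span these six timings and, for the untransformed bound, both standard error forms.

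| Rule once triggered | 5% loss | 8% loss | 10% loss |
|---|---|---|---|
| Crude alone | 2.2-3.2% | 2.2-3.9% | 2.2-4.6% |
| Either bound | 2.4-3.2% | 2.9-3.9% | 2.8-4.6% |
| Untransformed Kaplan-Meier alone | 2.4-3.2% | 2.9-3.5% | 2.8-3.6% |
| Log-log Kaplan-Meier alone | 2.2-2.7% | 2.0-2.2% | 2.0-2.2% |

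Two scenarios at 10% loss separate the causes:
- Even loss, 95% of events at the procedure: crude 2.2%, either bound 3.0-3.2%. The second sentence adds 0.8-1.0 points.
- First-week loss, half of events late: crude 4.6%, either bound 4.6%. The second sentence adds essentially nothing.

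Requiring both bounds gives 2.1-2.4% when events are early and up to about 3.6% with early loss and late events.

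**The case against.** The strongest defence is that the word *also* makes the Kaplan-Meier estimate supplementary, so the crude bound decides. That would hold if the estimate were only reported. But SAP 2.4.1 and 6.3.2 attach the success criterion to it, and the protocol's only success sentence comes after it.

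Several other objections stand:
- A reader might infer that the missing rule raises type I error to 4.6%. It does not. That value belongs to the crude bound alone, which counts lost subjects as event-free, under an event pattern the documents do not suggest. In the EU study the three subjects with Major Complications were those whose hemostasis took over 10 minutes, which points, on only three events, to early timing.
- A reader might take the crude denominator as settled at 263. SAP 6.3.2 supports that, but SAP 2.1 and Protocol 6.4 speak of 250 subjects available at 30 days, and not imputing is not the same as scoring event-free. If 14 lost subjects are dropped, 39/249 gives 20.78% and crude no longer passes at 39. The rules still differ: crude then allows 37 events, and Kaplan-Meier with all losses early allows 38.
- The label is partly handled. SAP 5.1 points to 2.4.1, and all three sections cite the same source, so a programmer would probably compute the same bound.
- Naming the untransformed Kaplan-Meier bound as sole decider does not by itself cure the excess when events are early.

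**Conclusion.** The gap is real and narrow. Above the trigger, the SAP as written lets either bound meet the primary safety objective, and no section resolves a disagreement. At or below the trigger the crude bound decides and there is no ambiguity.

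The excess attributable to the second sentence is about 0.2 points at 5% loss and 0.8 to 1.0 points at 8 to 10% loss when nearly all events are early. Across runs, about 2.1-2.4% becomes 3.0-3.3%. These figures rest on 263 treated subjects, lost subjects kept in the crude denominator, and the assumed timings and standard error forms. The planned sample size is unaffected. The label is a one-word correction. Severity: minor to should-fix.

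**What to change.** State one rule, in identical words, in SAP 2.4.1, SAP 6.3.2 and Protocol 8.3.3:

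1. With 13 or fewer subjects lost or dead of another cause within 30 days, the crude exact bound decides.
2. With more than 13, either bound alone must not suffice. Either (a) require both to be below 19.9%, or (b) name the Kaplan-Meier bound as sole decider.

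Option (a) removes the excess from the second sentence. Simulated power at 13% stays at about 84% or more. Option (b) with an untransformed bound leaves 2.8-3.6% at 8-10% loss, with power about 85-89%. If (b) is chosen, the log-log scale with Greenwood variance brings this to about 2.0-2.3%, with power about 81-85%, still above the planned 80%. That scale is the sponsor's choice. Neither option guarantees 2.5% when losses fall early but stay at or below the trigger: with 5% first-week loss and half of events late, the log-log rule gives 2.7%.

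Also state whether lost subjects stay in the crude denominator, call the Kaplan-Meier bound asymptotic everywhere, and use the 30-day trigger of SAP 5.1 throughout. At 263 the two SAP triggers already agree (13/263 = 4.94%, 14/263 = 5.32%), so that last edit is housekeeping. The cost is wording in three sections, with no change in sample size.
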